2.2 Benefit/Risk Assessment

More detailed information about the known and expected benefits and risks and reasonably expected adverse events (AEs) of RESP301 may be found in the Investigator's Brochure.

2.2.1 Risk Assessment

Table 2-1 Risk Assessment

Potential Risk of Clinical Significance	Summary of Data/Rationale for Risk	Mitigation Strategy
Study Intervention RESP301		
Participants may need to be discontinued from supplemental oxygen for	Study treatment is to be administered via a vibrating mesh nebulizer which is designed for oral inhalation.	Participants unable to be safely discontinued from supplemental oxygen will be

Potential Risk of Clinical Significance	Summary of Data/Rationale for Risk	Mitigation Strategy
several minutes to receive nebulized study treatment		
excluded (Exclusion criterion 2)
 
Treatment administration is to be performed as quickly as possible (Section 1.3)
 
Oxygen saturation (SpO₂) and heart rate will be monitored throughout the study intervention administration (Section 1.3)
 
In case of decrease in SpO₂ or clinical signs of intolerance to nebulization, RESP301 treatment may be paused temporarily and supplemental O₂ resumed or the study treatment may be discontinued permanently (see Section 7.1) per Investigator assessment.

Risk of methemoglobinemia	Very low levels are produced but as methemoglobinemia has been reported with continuous NO gas administration, the risk cannot be firmly ruled out	Participants with a history of methemoglobinemia will be excluded (Exclusion criterion 4), methemoglobin (mHb) level >2% is exclusionary (exclusion criterion 13), and mHb is included in safety laboratory tests (Section 1.3)

Potential Risk of Clinical Significance	Summary of Data/Rationale for Risk	Mitigation Strategy
Risk of clinical bronchial hyper-responsiveness related to nebulization	
Excipients in the nebulized RESP301 include mannitol which is a known bronchial irritant at the average dose of a positive mannitol test (239.0 ± 185.0 mg, Brannan et al, 2005). While the dose used in this study (54.66 mg) is lower than the average dose for a positive mannitol test, it has not yet been tested in COVID-19 patients and may potentially cause or exacerbate cough or bronchospasm in susceptible individuals in this specific population
	
Participants with a known history of moderate or severe bronchial hyperreactivity (such as in asthma) or presence of signs of significant bronchospasm on examination will be excluded from study participation (Exclusion criterion 5)
 
For the first 10 participants treated before the first Independent Data Monitoring Committee (IDMC) safety review (Section 9.6), RESP301 will be administered by intermittent inhalation until the intended dose is delivered (Section 6.1), so that the treatment can be quickly adjusted and rescue bronchodilator initiated if needed (Section 6.5.2)
 
After reviewing safety data, the IDMC will decide whether the intermittent inhalation of RESP301 can be replaced by continuous inhalation.

Potential Risk of Clinical Significance	Summary of Data/Rationale for Risk	Mitigation Strategy
Study Procedures		
Nebulization	The delivered dose of RESP301, estimated to be ~40% of the masses listed in Table 6-2, can be affected by patient technique and inspiratory capacity leading to inter- and intra-patient variation in actual doses of these ingredients, given the acute nature and high disease burden in this proposed clinical setting	Training will be provided to study staff to minimize variation in dose
Other		
Risk of spreading SARS-CoV-2	SARS-CoV-2 is known to be transmissible via respiratory droplets and any interventions that may potentially increase cough or aerosolization of respiratory secretions of an infected patient may increase risk of spread of disease	Proper personal protective equipment including appropriate mask, face shield, gown and gloves should be used at all times. When possible, the site staff should not remain in the room during study intervention administration (providing that continuous O ₂ monitoring can be conducted remotely and study intervention can be administered correctly)

2.2.2 Benefit Assessment

To date, no treatment of COVID-19 has demonstrated clinical efficacy. Patients and their physicians are critically in need for treatments that decrease the risk of severe levels of disease,

particularly the rate of intubation or other ventilatory support as they significantly lead to fatal outcomes. Considering the current pandemic, even a limited improvement in the rate of progression to severe stage of the disease would provide sizable benefits for patients and society.

Nitric Oxide is already marketed (e.g., INOmax®, NOXIVENT™, etc) in the United States (US) and other countries as a gas for continuous use in preterm and near-term (>34 weeks gestation) neonates with hypoxic respiratory failure associated with clinical or echocardiographic evidence of pulmonary hypertension in conjunction with ventilatory support and other appropriate agents. It is well tolerated, although under continuous use, a small number of cases of methemoglobinemia have been reported (NOXIVENT™ FDA Prescribing Information).

Nitric oxide has been shown in vitro to inhibit the replication cycle of severe acute respiratory syndrome coronavirus (Akerström S et al, 2005). In addition, NO is a naturally occurring and potent antimicrobial agent in the human body, which is active against viruses, bacteria, fungus, and yeasts (Fang, 1997). In particular, NO inhibits replication in vitro in a number of respiratory viruses including influenza A and B (Rimmelzwaan et al, 1999, Regev-Shoshani et al, 2013), human rhinovirus (Sanders et al, 1998), and respiratory syncytial virus (Ali-Ahmad D et al, 2003).

The ability of RESP301 to have a marked antibacterial action is highly relevant in the context of treating patients with SARS-CoV-2 infection since superimposed bacterial infection is a critical factor and a major cause of morbidity and mortality. RESP301 would restore and replenish the NO deficiency in patients who have succumbed to SARS-CoV-2 infection. RESP301 also has key advantages over inhaled NO gas, as discussed in Section 2.1.

A vibrating mesh nebulizer is advised for administration of RESP301. Amongst the suitable nebulizers, the device chosen for the study is a commercially available, CE-marked vibrating mesh device that delivers a mist of fine droplets in the size range required for pulmonary deposition (Mass Median Aerodynamic Diameter < 5 µm). This has been shown to be ideally suited for penetration deep into the alveolar spaces of the lung. As with all nebulizers in clinical use, there is a residual amount of drug that remains in the nebulizer so that not the full amount of drug is administered. The device operates continuously once initiated and automatically switch off once the medication has been delivered. The device may be used in pediatric and adult populations, as permitted by the prescribed medication, and is suitable for use in home environments or hospital/clinic settings.

As testing inefficient product would distract sites from participating in other research efforts, two interim analysis for futility purpose have been planned.

2.2.3 Overall Benefit: Risk Conclusion

Taking into account the measures taken to minimize risk to participants in this first-in-man study, the potential risks identified in association with RESP301 are justified by the anticipated benefits that may be afforded to participants with COVID-19.

3 Objectives and Endpoints

Table 3-1 Objectives and Endpoints

Objectives	Endpoints
Primary	

 To evaluate efficacy of RESP301 in preventing progression of hospitalized COVID-19 participants at level 3 or 4 in the modified World Health Organization (WHO) ordinal scale into higher levels. 	
 Proportion of participants who progress by at least one level higher on the modified WHO ordinal scale by Day 14
Key Secondary	

 To assess the effect of RESP301 as measured by room air SpO₂ 	
 Change in room air SpO₂ from baseline over time

 To assess the effect of RESP301 as measured by the National Early Warning Score (NEWS) 2 symptom score 	
 Change in NEWS 2 symptom score from baseline over time

 To assess the treatment response on clinical status 	
 Change from baseline on the modified WHO ordinal scale at each visit up to Day 28 Time to improvement of at least one level lower on the modified WHO ordinal scale Time to progression of at least one level higher on the modified WHO ordinal scale
Additional Secondary	

 To assess the treatment response on clinical status 	
 Time to hospital discharge Incidence of mortality by Day 28
Safety	

 To assess the overall safety profile of RESP301 in COVID-19 participants 	
 Clinical safety laboratory measurements Physical examinations

Objectives	Endpoints
	
• Vital signs• Concomitant medications• Counts and cumulative incidence of:
○ Adverse events (AEs)○ Serious adverse events (SAEs)○ Severe AEs

• To assess the ability of participants to tolerate nebulization	
• Incidence of participants unable to tolerate nebulization due to:
○ Reduction in SpO₂ to < 90%, unless well clinically tolerated according to Investigator's opinion○ Other clinical signs of intolerance according to Investigator's opinion• Incidence of clinical bronchial hyper-responsiveness related to nebulization
Exploratory	

• CCI	
• CCI

4 Study Design

4.1 Overall Design

This is an open-label, randomized, multicenter, parallel group, concurrent, controlled study in hospitalized participants with COVID-19 (WHO ordinal scale level 3 or 4) using a sequential adaptive design to evaluate the efficacy and safety of RESP301 added to standard of care (SOC). Approximately 300 adult (male and female) participants will be consented and randomized 2:1 to the Investigational arm or the Control arm. Participants randomized to the Investigational arm will receive inhaled RESP301 (6 mL) administered using a vibrating mesh nebulizer TID for up to 10 days in addition to the standard of care (SOC) while participants in the Control arm will receive SOC alone.

The study will be divided into the following periods:

- Screening period: starts up to 2 days (48 hours) prior to and extends up to the day of treatment initiation (Day 1); Days -2, -1 and 1

- Intervention period: up to 10 days; Day 1 to Day 10
- Efficacy follow-up: Day 14 and Day 28 (± 2 days)
- Safety follow-up: 28 days after treatment initiation; with the participant being contacted by phone call, if not still hospitalized, on Day 28 (± 2 days)

After screening, eligible participants will be randomized to either RESP301+SOC or SOC alone on Day 1, and the study treatment will be initiated as applicable (Table 1-1). Screening and randomization may happen on the same day (Day 1).

An individual administration of study intervention will be stopped, and supplemental oxygen resumed if applicable, if threshold limits of SpO₂ 89% or heart rate 120 beats/min (or as indicated by the Investigator) are exceeded (see Section 4.2 and Section 8.1.2). However, the participant may continue with subsequent doses if the Investigator judges that the benefit / risk ratio remains positive. In this case, the instruction to continue should be duly recorded in the participant's hospital file and the subsequent nebulization should be closely monitored.

Inhalation of study intervention should be completed within 20 minutes. A staggered dosing approach will be used for the first 10 participants (and enrolment up to completion of the first IDMC safety review) to monitor tolerability and response to RESP301 (see Sections 6.1 and 9.6).

The study treatment will be permanently discontinued prior to 10 days if the participant:

- Improves to level 1 or 2 of the modified WHO ordinal scale;
- Progresses to a level > 4 of the modified WHO ordinal scale;
- Experiences an event that requires permanent discontinuation as described in Section 7.1.

In the above cases, participants will be considered as ongoing in the study until the final Safety follow-up phone call (Day 28). Participants will be withdrawn from the study prior to Day 10 (Early withdrawal) only if they withdraw consent.

The total study duration for a participant from screening to last follow up will be up to 30 days (± 2 days).

Participants will be stratified by country and presence of risk factor(s) for severe outcomes of COVID-19, based on comorbidities and age, as detailed in Section 6.3.

Two interim analyses are planned (see Section 9.5 for details).

An IDMC will be responsible for closely reviewing the safety and efficacy data from the interim analyses and for providing their recommendations on continuation of the study. The IDMC will meet after 10, 20, 60 and 150 participants have completed the study (see Sections 9.5 and 9.6).

4.2 Scientific Rationale for Study Design

NO is a naturally occurring and potent antimicrobial agent in the human body which has been shown in vitro to inhibit replication of severe acute respiratory syndrome coronavirus (Akerström S et al, 2005), including SARS-CoV2, and other respiratory viruses. NO as an inhaled gas is already marketed in the US and other countries (see Section 2.2.2) but has disadvantages over NO produced locally in the oropharynx or lung airways (lengthy treatment requiring NO canisters, the inhaled NO is expelled in exhalation, the NO gas oxidizes in air to form toxic NO₂ which is a potential lung irritant and a contaminant in the patient's environment, and the half-life of NO in air is short).

RESP301 has potential advantages over inhaled NO gas:

- RESP301 demonstrates powerful evidence in vitro as a broad-spectrum anti-microbial;
- Treatment is quick, easy and portable using a standard handheld nebulizer;
- The formulation is nebulized and forms a fine particle mist that settles on the lung surface, at the point of infection, and is therefore a more targeted approach;
- NO production continues in-situ post treatment;
- Because of the design of the formulation, production of NO₂ is negligible by virtue of the NO₂ being rapidly converted to a NO donor species.

In this study, the effect of RESP301 as an add on treatment to SOC will be evaluated for its efficacy in reducing rate of progression to a more severe level of COVID-19 and for safety by comparison with SOC alone in hospitalized COVID-19 patients. A sequential adaptive design was chosen in order to assess futility and sample size after interim analyses (see Section 9.5). The study design was developed in accordance with the latest WHO and regional regulatory agencies guidelines.

Several risks factors for severe or fatal outcomes have been reported (Bialek et al, 2020; Huang et al, 2020; Novel Coronavirus Pneumonia Emergency Response Epidemiology Team, 2020; Rong-Hui et al, 2020; Zhou et al, 2020). To minimize bias, the results will be stratified according to the known risk factors as described in Section 6.3.

In this study, measures will be in place to trigger discontinuation of study intervention at a SpO₂ limit pre-agreed at the site (see Section 8.1.2). There is no critical level of oxygen saturation below which tissue hypoxia occurs due to the large number of variables that contribute to

hypoxia at the tissue and cellular level (temperature, pH, tissue blood flow). As a result, there is no consensus about what constitutes normal and abnormal oximetry (ATS/ACCP, 2003). To support and guide the team in charge of study intervention administration, a default value of SpO₂=89% and heart rate (120 beats/min) has been proposed as a suitable limit of tolerance. However, for the reason stated above, this limit can be overruled by the Investigator in either direction.

Newly released guidelines for ongoing clinical trials during the COVID-19 pandemic have emphasized the need to reduce the burden on sites and clinical trial personnel/investigators whether they be administrative, site visit, or other burdens (ACRO, 2020; EMA, 2020; HRS, 2020). Thus, without blinding and a placebo, along with minimal procedures, the additional burden on clinical staff has been reduced as much as possible.

4.3 Justification for Dose

Studies with nebulized sodium nitrite (AIR001) in healthy subjects and in patients have shown that inhaled nitrite produces dose proportional plasma pharmacokinetic without accumulation following repeated administration, with low systemic blood levels of nitrite and methemoglobin (<3%). Inhaled nitrite at doses up to 90 mg TID displayed a good safety profile and is well tolerated (Rix et al, 2015; Parsley et al, 2013; Simon et al, 2016).

In this study, 6.0 mL RESP301 (delivered dose 62 mg) will be administered via a vibrating mesh nebulizer, TID with at least 6 hours between each dose. Each 6.0 mL dose for nebulization contains the masses described in Table 6-2.

4.4 End of Study Definition

A participant is considered to have completed the study if he/she has completed the Treatment Period and the Follow-up Period (through the Day 28 EoS Follow-up). End of the study is defined as the last participant's last visit or follow up call.

5 Study Population

Prospective approval of protocol deviations to recruitment and enrollment criteria, also known as protocol waivers or exemptions, is not permitted.

The study population will consist of male and female COVID-19 patients, including pregnant women and women of child bearing potential. Participants must be able to provide written consent and meet all the inclusion criteria and none of the exclusion criteria.

5.1 Study Rationale

This is an open-label, randomized, multicenter, parallel group, concurrent, controlled study using a sequential adaptive design to evaluate the efficacy and safety of RESP301 plus SOC versus SOC alone in hospitalized patients with COVID-19 (WHO level 3 & 4).

Each constituent (see Section 6.2) of RESP301 is used as SOC for various conditions. Product application is straightforward, requiring a few minutes of inhalation using a standard nebulizer. RESP301 is likely to be beneficial in treating patients with COVID-19 who are not receiving ventilation but may be using supplementary oxygen in order to maintain a safe level of SpO₂.

Considering the well-established and global use of NO and the device, and the current public health emergency resulting from the COVID-19 pandemic, a Phase2/3 study of RESP301 is considered reasonable in order to generate efficacy data in patients infected with COVID-19.

5.2 Inclusion Criteria

Participants are eligible to be included in the study only if all of the following criteria apply:

Age

1. Participant is ≥ 18 years of age, at the time of signing the informed consent.

Type of Participant and Disease Characteristics

2. Participant has laboratory-confirmed SARS-CoV-2 infection as determined by reverse transcriptase polymerase chain reaction (RT-PCR) or other approved clinical testing prior to randomization.
3. Participant is hospitalized in relation to COVID-19 (WHO level 3 & 4).

Sex

4. Participant is male or female. All females of childbearing potential, including pregnant females, must consent to urine pregnancy testing at screening to be eligible for the study. (Females who are not of childbearing potential do not need to undergo a pregnancy test at screening).

Informed Consent

5. Participant is capable of giving signed informed consent as described in Appendix 1 which includes compliance with the requirements and restrictions listed in the informed consent form (ICF) and in this protocol.

5.3 Exclusion Criteria

Participants are excluded from the study if any of the following criteria apply:

Medical Conditions

1. Rapidly deteriorating or likely to require escalation to high flow oxygen, invasive or non-invasive ventilatory support within 24 hours according to Investigator's opinion.
2. Unable to safely receive a nebulized treatment for approximately 8 minutes according to Investigator's opinion.
3. Unable to receive or considered ineligible for invasive or non-invasive ventilatory support.
4. History of methemoglobinemia.
5. Uncontrolled asthma or history of severe bronchospasm.
6. Severe (requiring baseline oxygen therapy > 12 h/day prehospitalization) chronic respiratory disease (e.g., known COPD, pulmonary arterial hypertension, idiopathic pulmonary fibrosis, interstitial lung disease).
7. Suspected or confirmed untreated, active tuberculosis.
8. Severely immune-compromised participants in Investigator's opinion.
9. Recent (within 3 months) active coronary artery disease or decompensated heart failure (New York Heart Association class 3-4).
10. Presence of tracheostomy.

Prior/Concomitant Therapy

11. Chronic (≥ 4 weeks) use of corticosteroids >10 mg/day of prednisone or equivalent within 4 weeks of randomization.

Prior/Concurrent Clinical Study Experience

12. Participation in other clinical investigations utilizing investigational treatment or within 30 days / 5 half-lives whichever is longer.

Diagnostic Assessments

13. Clinically significant abnormalities in clinical chemistry or hematology at screening, defined as:
 - Methemoglobin level >2%
 - Platelet count <50,000 mm³
 - Alanine aminotransferase or aspartate aminotransferase >5 × upper limit of normal (ULN).
 - Estimated glomerular filtration rate <30 mL/min/1.73 m² (modification of diet in renal disease formula) or requiring hemofiltration or dialysis.

Other Exclusions

14. Anticipated transfer to another hospital which is not a study site during the treatment period.
15. Allergy to any of the components of the study intervention.

5.4 Lifestyle Considerations

No restrictions are required.

5.5 Screen Failures

Screen failures are defined as participants who consent to participate in the clinical study but are not subsequently randomly assigned to study intervention. A minimal set of screen failure information is required to ensure transparent reporting of screen failure participants to meet the Consolidated Standards of Reporting Trials publishing requirements and to respond to queries from regulatory authorities. Minimal information includes demography and reason for screen failure (e.g., eligibility requirements failed).

Individuals who do not meet the criteria for participation in this study (screen failure) may not be rescreened.

5.5.1 Screening and Enrollment Log and Participant Identification Numbers

The participant's enrollment will be recorded in the Screening and Enrollment Log.

Upon enrollment, each participant will receive a unique participant identification number. Participant numbers must not be re-used for different participants.

6 Study Intervention

Study intervention is defined as any investigational intervention(s), marketed product(s), placebo, or medical device(s) intended to be administered to a study participant according to the study protocol.

6.1 Study Intervention Administered

[figure not shown]
Table 6-1 Study Intervention(s) Administered

Study Treatment	RESP301 + SOC
Intervention Name:	RESP301
Type:	Drug
Dosage Formulation:	Admixture for inhalation
Unit Dose Strength(s):	Delivered dose (62 mg) sodium nitrite (NaNO ₂) (6 mL of NO-generating admixture of 150 mM NaNO ₂ , 50 mM mannitol and 100 mM citric acid)
Dosage Level(s):	One 6 mL-inhalation TID (every 8 hours) with at least 6 hours between 2 consecutive doses.
Route of Administration:	Inhalation
IMP and NIMP:	IMP
Sourcing:	RESP301 provided centrally by the Sponsor.
Dosing Instructions:	A vibrating mesh nebulizer will be used to administer the RESP301, under the direction of the study physician. Treatment is to commence within 5 minutes of RESP301 preparation. For the first 10 participants (and enrolment up to completion of the first IDMC safety review) RESP301 will be administered by intermittent inhalation to monitor tolerability and response to RESP301. After reviewing safety data, the IDMC will decide whether the intermittent inhalation of RESP301 can be replaced by a continuous inhalation. Before initiating each RESP301 inhalation, supplemental oxygen, if being used, will be interrupted for a few minutes until SpO ₂ levels are stable. Depending on the extent of SpO ₂ decrease, the RESP301 inhalation may be initiated or supplemental oxygen may be resumed at the discretion of the investigator. After treatment initiation, in case of SpO ₂ decrease, RESP301 inhalation may be paused and supplemental oxygen resumed. If the participant is unable to tolerate nebulization without supplemental oxygen, nasal oxygen may be administered during nebulization.
Packaging and Labeling:	Study intervention will be provided as two separate vials: NaNO ₂ /mannitol (3 mL) and citric acid buffered to pH 5.4 (3 mL), which will be labeled as required per country requirement.

Staggered dosing approach for the first 10 participants:

For the first 10 participants treated, and enrolment up to completion of the first IDMC safety review (Section 9.6), RESP301 dose will be administered in a staggered approach: after 2 minutes of inhalation, treatment is briefly paused to assess the participant. Provided there is no evidence of bronchospasm, treatment is continued for a further 2 minutes, after which treatment is again briefly paused for participant assessment. Thereafter, provided there is no evidence of bronchospasm and the participant is able to continue, the dose is completed (Figure 6-1), so that treatment can be quickly adjusted and rescue bronchodilator initiated if needed (Section 6.5.2). After reviewing safety data, the IDMC will decide whether the intermittent inhalation of RESP301 can be replaced by a continuous inhalation (see also Section 9.6). Due to the urgency of the pandemic, if participants become eligible for the study during the IDMC review of the first 10 participants then they may be recruited; however, their administration of RESP301 will be staggered in the same way as for the first 10 participants.

Figure 6-1: Staggered Dosing Approach for the First 10 Participants

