6.2 Preparation, Handling, Storage, and Accountability

6.2.1 Preparation of Study Intervention Product

RESP301 is prepared at bedside by mixing two sterile 3 mL solutions (one of NaNO₂/mannitol and one of citric acid buffered to pH 5.4). The solution is to be nebulized immediately or within 5 minutes post mixing as per the instructions given in the SoA (Table 1-1) and, for the first 10 participants, as in Section 6.1 above (staggered dosing). The first administration of study intervention should be provided under clinical supervision.

RESP301 is mixed in the nebulizer chamber before use following the steps below (see Table 6-2 for details of composition):

1. First the vial marked A (NaNO₂ and mannitol) is opened and its contents are poured into the nebulizer chamber.
2. Next, the vial marked B (citric acid) is opened and its contents are poured into the nebulizer chamber.
3. The nebulizer lid should be closed, and the nebulizer should be swirled gently for a few seconds to mix the two solutions. The nebulizer should not be inverted.

The inhalation of the medication should start within 5 minutes of mixing the solutions and the inhalation process should be complete within 20 minutes of starting inhalation.

This combined mildly acidified nitrite solution (6 mL) is inhaled through the mouth using a vibrating mesh nebulizer under the direction of the clinical team. The purpose of the acidified nitrite aerosol is to deliver NO to the participant. The delivered dose of RESP301, assessed via simulated tidal breathing is estimated to be ~40% of the masses listed below; it should be noted that delivered dose can be further affected by participant's breathing pattern and inspiratory capacity and so inter- and intra-participant variation in actual doses of these ingredients may vary, given the acute nature and high disease burden in this proposed clinical setting.

Table 6-2 Composition of Drug Product, Diluent and Admixture

	Material	Function	Quantity per vial
Drug Product	Sodium Nitrite	Drug Substance	62.10 mg
	Mannitol	Excipient	54.66 mg
	Sterile water for injection	Diluent	
	Total Volume		3.0 mL
Diluent	Citric Acid	Diluent	115.28 mg
	Sterile water for injection	Diluent	
	Total Volume		3.0 mL
Acidified Drug Product Mixture (RESP301)	Sodium Nitrite	Drug Substance	62.10 mg
	Mannitol	Excipient	54.66 mg
	Citric Acid	Diluent	115.28 mg
	Sterile water for injection	Diluent	
	Total Volume		6.0 mL

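### The protocol gives 62 mg as the delivered dose of sodium nitrite, but its own composition table and delivery fraction imply about 25 mg, roughly a 2.5-fold contradiction

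*Protocol*

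**What the plan says.** The current protocol (WHO grade 3 and 4 version) describes the dose of sodium nitrite in five places.

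- **Section 6.1, Table 6-1**, unit dose strength: "Delivered dose (62 mg) sodium nitrite", for 6 mL of an admixture that is 150 mM in sodium nitrite, 50 mM in mannitol and 100 mM in citric acid.
- **Section 4.3**: "6.0 mL RESP301 (delivered dose 62 mg) will be administered via a vibrating mesh" nebulizer, three times daily. The section then adds: "Each 6.0 mL dose for nebulization contains the masses described in Table 6-2". The paragraph before it cites inhaled nitrite at up to 90 mg three times daily as well tolerated.
- **Section 6.2.1, Table 6-2**: 62.10 mg sodium nitrite in the 3.0 mL drug product vial, and the same 62.10 mg in the 6.0 mL mixture.
- **Section 6.2.1**, text above that table: "The delivered dose of RESP301, assessed via simulated tidal breathing is estimated to be ~40% of the masses listed below".
- **Section 2.2.1, Table 2-1**, nebulization row: "The delivered dose of RESP301, estimated to be ~40% of the masses listed in Table 6-2".

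Section 2.2.2 adds that some drug stays behind in the nebulizer, so less than the full amount reaches the patient. The older protocol version bound into the same document carries the same conflict.

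**The concern.** The same term, delivered dose, is attached to two different quantities: 62 mg in Table 6-1 and Section 4.3, and about 40% of the Table 6-2 masses in Sections 6.2.1 and 2.2.1. If 62.10 mg is everything loaded into the nebulizer, 62 mg can be the delivered dose only if essentially nothing is lost, which three other places in the protocol deny.

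What is at stake is the exposure attached to the trial's results. Section 4.3 is the dose justification, and it sets a figure labelled as delivered beside a precedent of up to 90 mg. Section 2.2.3 calls this a first-in-man study and Section 8.6 says pharmacokinetics are not evaluated, so no planned measurement would show which exposure was achieved. A report that copied Table 6-1 would attach to the efficacy and safety findings, including a null result, an exposure that other sections of the protocol contradict.

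**Working it through.** **Inputs**

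- Concentrations and volume (Table 6-1): 150 mM sodium nitrite, 50 mM mannitol, 100 mM citric acid, 6 mL.
- Masses (Table 6-2): 62.10 mg, 54.66 mg and 115.28 mg respectively.
- Delivered fraction (Sections 6.2.1 and 2.2.1): about 40%.
- Stated delivered dose (Table 6-1, Section 4.3): 62 mg.
- Precedent (Section 4.3): up to 90 mg three times daily.
- Molar masses come from atomic weights, not from the protocol: sodium nitrite 69.0, mannitol 182.17, citric acid 192.12 g/mol.

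**Step 1. Does Table 6-2 hold the full loaded content?**
Loaded mass = concentration × volume × molar mass.

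| Component | Calculation | Result | Table 6-2 |
|---|---|---|---|
| Sodium nitrite | 0.150 mmol/mL × 6 mL × 69.0 mg/mmol | 62.10 mg | 62.10 mg |
| Mannitol | 0.050 × 6 × 182.17 | 54.65 mg | 54.66 mg |
| Citric acid | 0.100 × 6 × 192.12 | 115.27 mg | 115.28 mg |

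All three masses reproduce to within 0.01 mg. Table 6-2 is therefore the complete content of the 6 mL admixture, with no delivery loss applied.

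**Step 2. Can 62 mg be reproduced as a delivered dose?**
Delivered mass = loaded mass × delivered fraction = 62.10 × 0.40 = 24.84 mg. The stated 62 mg does not reproduce. It matches the loaded mass only: 62 / 62.10 = 99.8%, which would mean almost complete delivery.

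**Step 3. Size of the gap**
62 / 24.84 = 2.50. The 40% is itself approximate, so an assumed range is shown (the protocol gives none):

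| Delivered fraction | Delivered per inhalation | 62 mg relative to it |
|---|---|---|
| 35% (assumed) | 21.7 mg | 2.85-fold |
| 40% (protocol) | 24.8 mg | 2.50-fold |
| 45% (assumed) | 27.9 mg | 2.22-fold |

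Over three inhalations a day the two readings give 3 × 62 = 186 mg and 3 × 24.84 = 74.5 mg.

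**Step 4. The same conflict seen from the other side**
For 62 mg to be delivered at 40%, the fill would have to contain 62 / 0.40 = 155 mg. In 6 mL that is 155 / (69.0 × 6) = 0.374 mmol/mL, or about 374 mM, against the 150 mM in Table 6-1. This shows that the statements cannot be combined; it is not a suggested fill.

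**Step 5. Relation to the cited precedent**
62 / 90 = 69%; 24.84 / 90 = 28%. The protocol does not say whether the 90 mg is a loaded or a delivered dose, so neither percentage can be called like for like.

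**The case against.** The strongest reply is that little depends on the label. The regimen, 6 mL of a fixed admixture three times daily, is the same in Sections 4.1, 6.1 and 6.2.1. The primary analysis compares randomized arms in the intent-to-treat population, and no planned analysis uses delivered milligrams. A null result would strictly concern the regimen as given. This stands: there is no claim of bedside misdosing and no effect on power or alpha. How exposure is later interpreted is a separate matter, and there the label does count.

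Second, the protocol discloses the 40% and warns of variation within and between participants, and Section 4.3 points straight to Table 6-2. A careful reader can therefore find the conflict, but finding it does not resolve it. The stated unit dose strength and the dose justification still carry the other figure.

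Third, the 28% and 69% depend on the unstated basis of the 90 mg, and both readings lie numerically below 90 mg. That is right, and those percentages show only that the comparison lacks a common basis. The contradiction that can be established is the internal one, 62 mg against about 25 mg.

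Fourth, every mass in Table 6-2 is correctly calculated, and Table 2-1 also uses a full loaded mass for mannitol (54.66 mg) in its own safety comparison, so this may be a matter of terminology. That would explain how the conflict arose, but it would still need correcting. Reading Table 6-1 as the dose dispensed does not help either, because Section 6.2.1 uses the same term for the 40%.

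**Conclusion.** The concern holds. The current protocol contradicts itself on the delivered dose of sodium nitrite: 62 mg in Table 6-1 and Section 4.3, about 24.8 mg by Table 6-2 with the fraction in Sections 6.2.1 and 2.2.1. The gap is about 2.5-fold, or 2.2- to 2.9-fold over an assumed 35% to 45%. The result rests on the protocol's own composition and its own approximate delivery fraction, which was obtained by simulated tidal breathing and varies with the patient's breathing.

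This is more than clerical, because the disputed figure is the stated unit dose strength and is used in the dose justification. It should be corrected, but it does not threaten the primary analysis. Which figure applies is for the sponsor to state.

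**What to change.** Reconcile Table 6-1 and Section 4.3 with Section 6.2.1, Table 6-2 and Table 2-1. Wherever a sodium nitrite mass appears, label it as loaded (nominal) or delivered, and give the delivery fraction and how it was obtained beside any delivered figure. In Section 4.3, state whether the cited 90 mg is a loaded or a delivered dose and make the comparison on that one basis. Use the same labels in later reports of exposure.

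If the change is confined to labelling, the cost is a few lines in Table 6-1 and Section 4.3 plus a check of the cited source, with no change to what participants receive, to the sample size or to the analysis. The sponsor must decide which figure is correct; none is proposed here.
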